## C.6. Analytic Plan.

**General strategy.** Three waves of data will be collected (baseline/enrollment, 6 and 12- months of intervention). Analyses will be carried out according to the intention-to-treat rule consistent with standard practice in most clinical trials. We will conduct standard statistical diagnosis and descriptive statistics of demographic and background variables, and examine frequencies for reasonableness, sparseness (categorical data) and non-normality (continuous variables) of the data. Missing data will be addressed using multiple imputation and/or full information maximum likelihood estimation. Psychometric properties of the study scales will be investigated to ascertain appropriate validity and reliability. Preliminary analyses will test group equivalence on baseline characteristics. Categorical methods of analysis (e.g., cross tabulations, chi-square) will be used for discrete data while *t*-tests will be used for continuous data to test the comparability of the prevention arms. Factors found to be different at baseline will be adjusted for in subsequent analyses. The following **covariates** will be entered in all analyses: home visitor, home visitor experience (years), number of visits, household composition, race/ethnicity, acculturation, mother's age, medical history/gestational diabetes, post-partum depression.

**Social network analysis (SNA).** Network data will be analyzed using SNA packages in R (e.g., SNA, igraph) to produce visualizations and statistics that summarize the characteristics of each mothers' network. We will compute the following network statistics: the proportion of network members that provide specific types of health relevant support, and that engage in specific health behaviors; and the density of supportive relationships within each network (i.e., the number of supportive relationships among network members that are reported, as a proportion of the total number of possible supportive relationships where all network members provide support). These statistics will be computed for each assessment period (as well as change statistics across periods), and included in the analyses, as described below.

**Statistical Models Aims 1-3.** Our conceptual model includes three types of variables: Intervention arms (HVP vs. HVP+COPE) and covariates, mediators, and outcome variables. We will use multiple statistical procedures tied to the analytic objectives of each of our specific aims, including generalized linear modeling, path analysis and structural equation modeling (SEM) approaches. To control for potential cluster effect due to home visitors as families are nested with visitor, statistical models will be developed based on multilevel path analysis to test direct and indirect (or mediational) effects hypothesized in the model. The models involve two levels with mothers or children as Level-1 units and visitors as Level-2 units treated as a random effect. With multilevel path modeling approach, the covariance matrix to be analyzed can be properly decomposed into individual- and group-level covariances to account for the clustering effect due to visitor nesting effect of the data. The multilevel path model can involve all variables from the family level in the analysis. The model can also incorporate distal predictors and mediators from the visitor-level (Level-2) and outcomes from family-level (Level-1) data. The aims of the proposed study focus on the Level-1 units. Following Bentler-Weeks modeling notation, the path model can be expressed as:  $\eta = \beta\eta + \gamma\xi$ , with all exogenous (distal) variables defined as  $\xi$  and all endogenous (mediators and final outcomes) variables as  $\eta$ . The parameters in  $\beta$  and  $\gamma$  matrices can be specified according to the hypotheses of each Aim. Models to be developed are discussed in greater detail below for each Aim. Mplus software will be used model estimation and evaluation.

**Aim 1 (maternal/infant outcomes).** Change in weight-related outcomes over the 2-year implementation is the primary outcome comparison. We will use multilevel regression models adjusting for clustering effect of home visitors to compare differences in the main outcomes across time by intervention arm. Regression model can be treated as a special case of path model without mediators. These regression models will include all participants, who have at least 2 measurements, regardless of when the measurements are taken, increasing the follow-up of study participants and statistical power. Specific measures relevant to Aim 1 are maternal and children weight-related measures. These models will allow the evaluation of intervention effects on, for example, child growth trajectory and activity, and mother BMI, metabolic, and behavior outcomes. Investigation of the main effects of COPE on outcomes will be conducted at each follow-up. Baseline outcome measures will be treated as covariates to control for potential

baseline differences. Effects of COPE will be evaluated first at each follow-up assessment point. Longitudinal analyses with all follow-up points (6 and 12 months) will then be conducted to examine profiles across time to investigate the effects of program conditions on trends of outcome measures.

**Aim 2 (maternal transmission).** To estimate the mediational effects of maternal transmission, multilevel path models will be developed and evaluated per our hypotheses. The model specification will be guided by our conceptual model treating Intervention program as the distal variables along with demographic variables to affect mother's weight, diet and behavior as mediators, which in turn may influence infants' outcome. While the intervention program will be at the Level-2 unit, all other variables included in the multilevel path models will be Level-1 variables obtained from mothers and children. Using breastfeeding and maternal diet on infants' weight trajectories as an example, the mediation mechanism of maternal transmission can be expressed by the process: COPE → breastfeeding \* maternal diet → weight. The path model will allow the test of both the direct effect of COPE on infant weight trajectory and its indirect effect on through breastfeeding and maternal diet.

**Aim 3 (social transmission).** A multilevel path model similar to the one described in Aim 2 will be specified. Mediators can be specified in a process to more appropriately represent the mechanism of social transmission. For example, the model can contain a sequence of influences such as: COPE → density of social network support → maternal outcomes → infant outcome. A direct effect of social network on infants' outcomes can also be specified to investigate if social network has direct and indirect effect on infants' outcomes.

**Power Analysis Aims 1-3 (Figure 7).** A total of 30 home visitors will be recruited and randomized to HVP or HVP+COPE. With an average of 13 families served by each visitor, a total of 300 families will be invited to participate in the proposed study over 12 months. Based on our pilot work and existing HVP data, we expect a retention rate of 75% of families, which will result in a final sample of 200 mothers/infants. We have calculated power using G\*Power based on an effective sample of N=200 for the main weight related outcomes with the design of repeated measurement. All tests use a two-sided alpha level of .05. Our pilot study showed a small to medium effect size of .4 (Cohen's *d*) on our main outcome of children's weight velocity and smaller effect on energy intake at 6 months post-test. No previous study has investigated the long-term (12 months) delivery of in-home obesity prevention on 0-2yo children's growth trajectory, diet and activity. However, an in-home intervention compared to outpatient pediatric counseling resulted in a large effect size of 1.64 (Cohen's *d*) for changes in zBMI at 12 months, among obese 2-5yo children. To account for potential large clustering effect at the home visitor level, we assume the intraclass correlation (ICC) of .05 to .1 with inflation factors  $(1+(n-1)*ICC)$  of 1.4 to 1.8, respectively. After taking inflation factor into account, our proposed sample size of 200 will have enough power to detect medium effect sizes based on Cohen's *f* between .17 and .20. More comprehensive path model will be specified in each aim for model evaluation and hypothesis testing. We are aware of the sample size limitation and will be cautious in the number of variables and the size of the model involved. We used the hypothesis-testing framework of RMSEA to estimate power of model fitting in our study. With  $\alpha = .05$ , a null hypothesis RMSEA of .00 (almost exact fit for path model), an alternative hypothesis RMSEA of .08 (criterion of not acceptable models) and degrees of freedom (size of the model) ranging from 10 to 15, the range of statistical power for a sample size of 300 is between .83 and .93. We will have sufficient power to detect small to medium effect of a set of pre-selected parameters associated with mediators and outcomes with sample size of 200.

**Secondary Aim (Real-life economic analysis).** We will document the costs of adding COPE to HVP's services through cost logs and interviews with HVP directors. We will consider the costs of labor (the time home visitors spent in training and in administering COPE, times their wage rate) and of materials (training and intervention manuals for home visitors), and evaluate how these costs can be absorbed through the ongoing funding from the Affordable Care Act. We will calculate infants and mothers' weight, metabolic, and behavioral trajectories and how they differ by child gender, household structure, and other observables. These analyses will be conducted at two levels. First, we will calculate the cost-effectiveness of HVP+COPE (vs. HVP only) by comparing the cost of adding COPE per unit of improvements in weight, metabolic, or behavioral outcomes with the cost per unit of improvement in these outcomes vs. alternative obesity programs with similar aims (e.g., prevention delivered in outpatient settings). This will provide a measure of the effectiveness of COPE vs.

[figure not shown]

Figure 7. Required sample size by effect size

alternative interventions. We will rely on an extensive review of the literature to obtain estimates of costs and improvements associated with such alternative programs. Second, in the absence of long-term data, simulation models are often used to predict long-term outcomes and/or evaluate the cost-effectiveness of healthcare interventions. We have developed a simulation model to predict BMI trajectories and associated medical expenditures over the life cycle (e.g., ). The model utilizes data from the Medical Expenditure Panel Survey (MEPS) to model yearly changes in BMI and healthcare costs associated with each possible initial BMI state. The model was validated using data from the National Health and Nutrition Examination Survey (NHANES). This work shows that reducing by 10% the risks of overweight/obesity (BMI  $\geq$  85th percentile) in ages 2-18 is associated with reductions in direct medical costs between \$2,830 (men) and \$3,000 (women) in adulthood. Reducing obesity risks by 25% is associated with savings of \$5,860 and \$6,022 in adult men and women respectively. We will use this model to predict reductions associated with long-term BMI and medical care expenditures over the life cycle and compare these to costs associated with COPE.

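### Extra covariates are picked by baseline significance tests that ignore visitor clustering: the treatment test is not inflated, but the model is left open and precision is lost

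*Combined protocol and SAP*

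**What the plan says.** Section C.6, general strategy, sets out a baseline screen: "Preliminary analyses will test group equivalence on baseline characteristics". For the discrete factors, "Categorical methods of analysis (e.g., cross tabulations, chi-square) will be used for discrete data while" t-tests serve the continuous ones, and both are meant "tests will be used for continuous data to test the comparability of the prevention arms" in the same sense. The consequence follows at once: "Factors found to be different at baseline will be adjusted for in subsequent analyses". No candidate factors are listed, no threshold is given for this step, and clustering is not mentioned.

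Two other provisions fix covariates whatever the screen shows. The same section names nine that "will be entered in all analyses: home visitor, home visitor experience (years), number of visits, household composition, race/ethnicity, acculturation, mother's age", followed by medical history/gestational diabetes and post-partum depression. The Aim 1 paragraph adds the baseline value of the outcome: "Baseline outcome measures will be treated as covariates to control for potential" baseline differences.

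Clustering is dealt with in the paragraph on statistical models for Aims 1-3, which introduces multilevel models with the visitor as a random effect: "To control for potential cluster effect due to home visitors as families are nested with visitor". That provision is written for the outcome models, not for the preliminary tests. Section C.3 confirms that visitors are the unit of randomisation.

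**The concern.** Two things are wrong with the screen.

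- **It selects on the wrong criterion.** A covariate earns its place by predicting the outcome. A significance test of baseline difference measures the imbalance that happened to occur. It can bring in a factor that has nothing to do with the outcome and leave out a strong predictor that is well enough balanced to pass.
- **It is mis-sized for this design.** Families of one visitor are treated as independent although whole visitors are allocated. Section C.3 also matches families to visitors on culture and language, which gives some baseline factors a reason to cluster.

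At stake are a fully specified main model and some precision, in a trial with only 30 randomised units.

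**Working it through.** **Inputs.** From the power analysis in C.6: 30 visitors, 300 families, average caseload 13, ICC .05 to .1, inflation factors 1.4 to 1.8, two-sided alpha .05. Assumed: 15 visitors per arm (the ratio is not stated), the planning ICC applied to baseline factors, and the .05 level applied to the screen.

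**1. The plan's inflation factor.** With DE = 1 + (n − 1) × ICC, the stated values require n = 9:
- 1 + 8 × .05 = 1.4
- 1 + 8 × .10 = 1.8

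The document gives no cluster size of 9. Its own sizes give:
- 300/30 = 10 families: 1.45 and 1.90
- caseload 13: 1.60 and 2.20
- 200/30 = 6.67: 1.28 and 1.57

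**2. True size of the screen.** Size = 2 × [1 − Φ(1.96/√DE)].

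| Families per visitor | ICC .05 | ICC .10 |
|---|---|---|
| 6.67 | 8.4% | 11.7% |
| 9 (implied by 1.4 and 1.8) | 9.8% | 14.4% |
| 10 | 10.4% | 15.5% |
| 13 | 12.1% | 18.6% |

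Worked for the plan's own factors: 1.96/√1.4 = 1.66 gives 9.8%; 1.96/√1.8 = 1.46 gives 14.4%. A simulation with 15 visitors per arm and n = 9 agrees: 9.9% and 14.6% for the t-test, 9.6% and 14.4% for chi-square at 30% prevalence. A t-test on visitor means holds 5.0%.

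**3. Sensitivity to the borrowed ICC**, at n = 10: ICC .01 gives DE 1.09 and size 6.0%; ICC .02 gives DE 1.18 and 7.1%; ICC .20 gives DE 2.8 and 24%.

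**4. How often something is flagged by chance.** P = 1 − (1 − size)^k for k independent factors. The count is assumed, because the plan lists none.

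| k | True 5% test | DE 1.4 | DE 1.8 |
|---|---|---|---|
| 5 | 23% | 40% | 54% |
| 10 | 40% | 64% | 79% |
| 15 | 54% | 79% | 90% |

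**5. Effect on the treatment comparison.** Simulation with 30 visitors, 10 families each, one covariate outside the fixed list, d = 0.4 (the pilot effect in the power section), and assumed covariate-outcome correlations of 0.3 and 0.5:
- With no treatment effect, the size of the treatment test after screening was 3.9% to 5.0%.
- At correlation 0.5, power with screening against always adjusting was 81% against 90% (ICC .05) and 71% against 80% (ICC .10), so about 9 points.
- At correlation 0.3 the loss was about 3 points.
- A separate simulation analysing visitor means gave losses of about 2 points at 0.3 and 7 to 9 points at 0.5.

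The loss arises because the screen, at n = 10, leaves the covariate out in 100 − 10.4 = 89.6% to 100 − 15.5 = 84.5% of trials, however well it predicts the outcome.

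**The case against.** The strongest reply is that the screen is only preliminary. The treatment effect is tested in a multilevel model with the visitor as a random effect, and nine covariates plus the baseline outcome enter regardless. **This stands, and it limits the point.** In a further simulation with 15 baseline factors, the naive screen and a mixed model, the treatment test had size 2.8% to 5.3% and the estimate was unbiased. A reader might infer from a screen with two to three times its nominal error that the trial's own false-positive risk is raised to match. Neither the documents nor the simulations support that.

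The ICC is also borrowed. The power section gives it as a planning value, not for baseline factors, and the factors most tied to culture and language (race/ethnicity, acculturation) are already fixed. **This stands:** with little clustering the excess is only one or two percentage points.

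A reader might blame clustering for a near-certain false flag. That does not follow: the candidate count appears nowhere in the plan, and a correctly sized test on 15 factors would still flag at least one 54% of the time.

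It may be said that surplus terms exhaust the degrees of freedom of 30 visitors. The harm is small: adding all 15 non-prognostic factors raised the standard deviation of the estimate only from .140-.142 to .145-.147.

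Finally, imbalance here need not be pure chance. Mothers are invited after six months of services (C.3), and the recruitment text under Protection of Human Subjects has home visitors introduce the study, although C.3 gives that task to assessment workers. **This stands** as a reason to look at balance and to examine adjusted results. It does not justify a significance rule, because a non-significant test does not show that the arms are comparable.

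**Conclusion.** The concern holds in a limited form. The rule is explicit, its tests ignore the randomised unit, and their true size is about 10% to 14% at the plan's own inflation factors, if the planning ICC and the 5% level apply to this step. At ICC .01 to .02 and 10 families per visitor it is 6% to 7%.

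The consequence is not a false-positive problem. The additional covariates cannot be named until the data are seen, the treatment test becomes slightly conservative, and precision is lost: about 3 power points at a correlation of 0.3 and about 9 at 0.5, both correlations being assumed. It would also be too strong to read the whole main model as unspecified, because the screen can only add to a fixed core.

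Even a cluster-adjusted screen would leave the model data-dependent, so correcting the test alone is not enough.

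**What to change.** In the general strategy of C.6:

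1. Delete the sentence that adjusts later analyses for factors found different at baseline, together with the baseline significance tests.
2. Keep the baseline outcome and those listed covariates that are genuinely measured at baseline. Add in advance any further prognostic baseline variables already collected, for example infant sex, and infant age where the outcome is not age-standardised. The plan describes no site or language stratum in the randomisation, so none should be added as if it did.
3. Present baseline characteristics descriptively, by arm and by visitor, without p-values.
4. Where an observed imbalance raises concern, including one that recruitment might have caused, report an adjusted result as a labelled sensitivity analysis beside the pre-specified one.

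The cost is a change of wording in the analysis plan, made before outcome data are examined. It needs no new data, visits or participants. Label: free improvement.

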*The proposed study builds upon the momentum, resources, and research infrastructure of our pilot work to test the larger-scale and sustained impact of COPE on infant's and mothers' obesity outcomes, and to study key mechanisms of maternal and social transmission on infants' obesity risk.* Specifically, 300 low-income mothers/infants enrolled in Healthy Families America HVP will be recruited and enrolled in the study, for an effective final sample of 200 mothers/infants. Based on standard HVP procedures, mothers/infants will be matched to highly trained home visitors (nurses) based on their ethnicity/race and language preferences. Home visitors, in turn, will be randomly assigned to deliver the standard HVP curriculum only or the standard HVP curriculum + COPE as part of their weekly home visits for two years of HVP services. Comprehensive assessments of mothers/infants will be conducted at enrollment and after 6 and 12 months of intervention.

**Specific Aim 1 (maternal and infant outcomes).** Test the direct effects of COPE on infants and mothers' weight, metabolic risks, diet/energy intake, and physical activity. This will be accomplished by comparing changes in body weight, metabolic markers, and eating and activity-related behaviors between infants/mothers across study arms (HVP only vs. HVP+COPE). These results will indicate whether HVP is an effective infrastructure for primary and secondary obesity prevention.

**Specific Aim 2 (maternal transmission).** Test whether breastfeeding and maternal diet and activity, feeding practices, and food insecurity mediate the effect of COPE on infants' outcomes. This aim will test mechanisms of maternal transmission on infants' obesity risks.

**Specific Aim 3 (social transmission).** **Aim 3** is two-pronged. **Aim 3a** tests the direct effect of HVP+COPE (vs. HVP only) on the characteristics of the social and community networks that surround mothers and infants (i.e., the density, composition, and quality of "health support networks"). **Aim 3b** tests whether the characteristics of social networks mediate the effects of COPE on maternal and infant outcomes. These findings will indicate if HVP obesity prevention efforts can alter and/or activate social network mechanisms.

**Secondary Aim.** Conduct a real-life economic analysis (costs, cost-savings, and non-monetary benefits) of integrating COPE into existing HVPs.

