**C. APPROACH**

This research is designed to integrate and leverage our team’s expertise (**Table 1**), as detailed in the *Personnel Justification* section, *Multiple PI Plan*, and *Biosketches*.

**C.1. Design overview.** **Table 2** depicts the logic model of the proposed study, and demonstrates its scientific rigor. Healthy Families America home visitors (see *Intervention arms* below for their qualifications) will be randomized to deliver the HVP curriculum with or without COPE for 12 months (standard HVP duration). Mothers/infants will be recruited and enrolled on a rolling basis over 24 months (study months 6-30), and

matched to a home visitor based on race, ethnicity and language preferences. Assessment of mothers and infants will be conducted by *assessment workers* (who are blind to study assignment) at enrollment, and after receiving 6 and 12 months of services. \*\*

	[name]	[name]	HFA	[name]	[name]	[name]	[name]
Infants and early childhood obesity/nutrition	x		x	x	x		
Home visitation services			x				x
Family-based behavioral obesity interventions	x						
Underserved, racial/ethnic populations and culturally/linguistically tailored interventions			x	x	x		x
Multilevel interventions for behavior change	x	x					
Social network measurement and analysis		x					
Longitudinal modeling of multilevel data		x				x	
Cost analyses of childhood prevention efforts							x

The assessment of participants after they ceased to receive services for a given period of time (i.e., “true” follow-up) is impossible because of the ongoing nature of HVP services. We believe that asking home visitors to withhold the delivery of the COPE material to allow for a “no COPE” period would be unrealistic in terms of potential contamination, and also create an uncomfortable situation for families and HVP staff.

SITUATION: More than 40% low-income children enrolled in federally funded programs are overweight or obese by age 5. Obesity efforts have limited impact among underserved, low-income children, at risk for obesity.		
INPUTS	OUTPUTS	OUTCOMES

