
**C.3. Participants.** Participants will be low-income mothers/infants (6mo at enrollment) *who are already receiving services from our HVP partner (Figure 6)*. Thus, study enrollment does not require that we recruit more families than our HVP partner is already enrolling. Mothers are enrolled in HVP services through outreach and screening pre-partum, in English or Spanish, at community health centers and hospitals. In order to be eligible mothers must meet a number of (but not all) risk criteria (e.g., low-income, housing instability). Enrolled mothers are matched to a home visitor (nurse) based on culture and language. **Recruitment.** Assessment workers (distinct from home visitors delivering services) who enroll families into services will introduce the study to mothers and obtain written consent. They will clarify with mothers that their refusal to participate in the study will not affect their receipt of any other services provided by the HVP. In our experience, families feel comfortable refusing if they are not willing to participate. Mothers/infants will be ineligible if they have any of the following conditions: eating disorders (e.g., bulimia nervosa), schizophrenia, and obesity-related syndrome (e.g., Prader Willi). Participants enrolled in a weight-loss program will be ineligible. Based on our pilot work, we expect to recruit 70% Hispanic/Latino, 13% African American, 8% White, 5% American Indian/Alaskan, 4% mixed race. **Retention.** We have learned a great deal about retention through our pilot work. For instance, most attrition from HVP services occurs in the first six months of services. Therefore, to maximize retention, mothers will be invited to participate in the study *after six months of home visits*. The unique relationship between home visitors and mothers facilitates subsequent retention, as many of these mothers are socially isolated and home visitors are important confidants and supports. We will use multiple strategies that are effective for high-risk populations to further retain the study sample: (1) gift cards of \$25 at each data collection, with all incentives paid after each assessment; (2) frequent contacts to maintain engagement and foster open communication; (3) quarterly newsletters to update subjects about study activities; (4) acknowledging birthdays and milestones; (5) reminder phone calls the day before the weekly visits and assessment sessions. **Randomization.** Randomization will be at the level of home visitors, who deliver the HVP (cluster randomization). Home visitors who serve mothers that are participating in the proposed study will be randomly assigned to deliver either HVP only or HVP+COPE. Potential concerns with randomizing by home visitors are feasibly addressed in this study. First, the likelihood of

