**C.5. Measurements.** HVP *Assessment Workers* (registered nurses who can draw blood) who enroll families into standard HVP services, have been trained to screen and recruit eligible families for the proposed project. They will administer the assessments (English or Spanish; **Table 6**) in the families’ homes or at the HVP clinic (as needed) at baseline/enrollment, and after 6mo and 12mo of services. *Home visitors* will be trained to gather interim (objective) weight measurements for the purpose of generating more frequent data points, triangulated with the assessment workers’ measurements.

**Medical and family history.** A thorough family history and physical examination will be conducted at baseline. We will collect demographic data, including socioeconomic status (education, income, eligibility for SNAP).

**Infant growth & waist trajectories.** Weight will be measured on a digital scale (Tanita) accurate to the nearest 5g. Length will be measured to the nearest 0.1 cm using an infanto-meter using the standardized WHO approach,

Table 6. Assessment time points (month of intervention) and key measures							
	Baseline	3	6	9	12	15	18
COVARIATES							
Demographics, household composition, medical history, post-partum depression, activity readiness	X						
MOTHERS							
Weight/height, waist circumference	X	X	X	X	X	X	X
Blood and vitals	X						X
24h diet & activity recall	X		X				X
Feeding and food insecurity	X		X				X
Social support and networks	X		X				X
Home environment	X		X				X
INFANTS							
Weight/length, waist circumference	X	X	X	X	X	X	X
Blood (finger prick)	X						X
24h diet & activity recall (from mother)	X		X				X

including use of staff training modules. Weight and length will be used to calculate weight-for-length and weight-for-age z-scores (WHO Standards), as recommended by the CDC for children <24 mos. Infant growth rates will be examined as the change in WLZ from baseline to follow up (12mo) Waist circumference will be measured at the umbilicus (nearest 1-mm) using a non-stretch measuring tape.

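### Adjusting every analysis for number of visits, with no counting window, can turn the primary comparison into an effect at fixed dose instead of the intention-to-treat effect

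*Combined protocol and SAP*

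**What the plan says.** C.6, General strategy, states: "Analyses will be carried out according to the intention-to-treat rule consistent with standard practice in most clinical trials". Later in that paragraph it names covariates that "will be entered in all analyses: home visitor, home visitor experience (years), number of visits, household composition, race/ethnicity", followed by acculturation, mother's age, medical history and post-partum depression. Number of visits appears nowhere else in the analytic plan, and no counting period is attached to it.

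C.6, Aim 1, makes change in weight-related outcomes the primary comparison. It adds the baseline outcome as a covariate and neither removes nor redefines number of visits. On who is analysed it says: "These regression models will include all participants, who have at least 2 measurements, regardless of when the measurements are taken".

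Other sections bear on what the count could be:

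- **Delivery.** Section A has visitors deliver "the standard HVP curriculum + COPE as part of their weekly home visits for two years of HVP services". C.1 says visitors "will be randomized to deliver the HVP curriculum with or without COPE for 12 months (standard HVP duration").
- **Entry.** C.3 (Retention) says "Therefore, to maximize retention, mothers will be invited to participate in the study" once six months of home visits have passed. C.1 adds: "Mothers/infants will be recruited and enrolled on a rolling basis over 24 months (study months 6-30").
- **Interim weights.** C.5 has home visitors trained "to gather interim (objective) weight measurements for the purpose of generating more frequent data points". Table 6 schedules weights at month 3 and every three months up to month 18.
- **Dropout.** Protection of Human Subjects, section C, expects 25% of mothers to leave home visiting over the 12-month study. C.2 reports considerably lower pilot dropout with COPE, without giving rates.

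**The concern.** Randomisation protects the comparison only for quantities fixed before assignment. Visits received during the intervention come after it and are the channel through which COPE reaches the family. If COPE keeps families in the service longer, as the pilot remark suggests it may, extra visits are part of its effect. Holding visits equal removes that part. If unmeasured engagement drives both attendance and outcome, conditioning on attendance also introduces a non-causal association between arm and outcome.

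Families would still be analysed in their assigned arm, but the coefficient would no longer estimate the effect of assignment. Because the window is open, the meaning of the primary estimate depends on a choice made later, possibly with the data in hand.

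**Working it through.** The plan states no figure on this point, so there is none to reproduce. The check has two parts.

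**1. Which windows do the documents permit?**

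| Window | Source | Status |
|---|---|---|
| Six months before study entry | C.3 | Baseline only if it also precedes any influence of the visitor's assignment |
| 12 months of intervention | C.1, C.2 | Post-randomisation |
| To month 18 | Table 6, Table 7 | Post-randomisation |
| Two years | A, C.6 Aim 1 | Post-randomisation |

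Table 6's baseline covariate row does not name visits. That does not settle the matter, because the row also omits acculturation and visitor experience, both of which are in the C.6 list. The first window is not automatically safe either. Visitors are the randomised unit and families enter on a rolling basis, so some families' six pre-entry months may follow their visitor's assignment.

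**2. How large could the shift be?** This is an illustration only.

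*From the documents:* weekly visits for 12 months (52) and 25% dropout overall. *Assumed:* dropout spread evenly over time, no missed visits while in the service, the split of dropout by arm, and the visit slope.

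In a linear model, adjusted effect = total effect − (pooled within-arm visit slope × visit gap). Let p be the dropout proportion in an arm. Among families still in the service at week w, let L = 52 − w and q = p(1 − w/52)/(1 − p·w/52). Then mean visits = 52 − qL/2 and variance = L²(q/3 − q²/4).

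Example, all families (w = 0), dropout 35% control and 15% COPE:

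- Gap = 26 × (0.35 − 0.15) = 5.2 visits.
- Variances: 901.33 × 0.35 − 676 × 0.35² = 232.7 (control) and 901.33 × 0.15 − 676 × 0.15² = 120.0 (COPE).
- Pooled SD = √176.3 = 13.3, so the gap is 5.2/13.3 = 0.39 SD.
- With an assumed slope of 0.2 SD per SD of visits, the shift is 0.2 × 0.39 = 0.08 SD.

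Gap, COPE minus control, in visits (SD):

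| Control/COPE dropout | All families | Reaching month 3 | Reaching month 6 | Completing 12 months |
|---|---|---|---|---|
| 25/25% | 0 | 0 | 0 | 0 |
| 27.5/22.5% | 1.3 (0.10) | 0.8 (0.09) | 0.4 (0.08) | 0 |
| 30/20% | 2.6 (0.19) | 1.7 (0.18) | 0.85 (0.16) | 0 |
| 35/15% | 5.2 (0.39) | 3.3 (0.36) | 1.7 (0.32) | 0 |
| Largest shift at slope 0.2 | 0.08 SD | 0.07 SD | 0.06 SD | 0 |

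The month-3 column matters because the Aim 1 rule needs only two measurements. Baseline plus a month-3 weight could qualify a family that left after about 13 weeks.

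*Direction.* If more visits go with better outcomes, the shift is toward zero. If families in difficulty receive more visits and do worse, the same sizes apply away from zero. If only COPE visits act, the pooled slope is 0.2 × V_COPE/(V_COPE + V_control), where V is the visit variance in each arm. That is 0.06 to 0.10, and the shift is at most 0.03 SD.

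*Yardstick.* SE = √(4 × inflation/N). With 200 families over 30 visitors (6.7 each), inflation is 1 + 5.67 × 0.05 = 1.28 to 1 + 5.67 × 0.10 = 1.57. The SE is then 0.16 to 0.18 SD, or 0.14 to 0.15 if multiplied by √0.75 for an assumed baseline correlation of 0.5. With the plan's own inflation of 1.4 to 1.8 and no baseline adjustment it is 0.17 to 0.19.

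*Simulation checks.* One used 30 visitors, 200 families including dropouts, a random visitor intercept, baseline correlation 0.5 and a true total effect of −0.40 SD. Without visits in the model, the estimate stayed at −0.39 to −0.40. With visits and a slope of −0.2, the four splits gave −0.40, −0.38, −0.36 and −0.32. With slope +0.2 they gave −0.40, −0.42, −0.44 and −0.48.

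A second, unclustered check used stronger assumed values. A visit gap of 0.5 SD and a slope of −0.4 moved −0.40 to −0.20. With no effect of visits at all, but a shared unmeasured cause, −0.40 moved to −0.32.

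**The case against.** The best counter-argument is that a baseline count is meant. The list follows directly on a sentence about adjusting for baseline differences, most family-level items in it are background characteristics, and a six-month pre-entry history exists for every family. On that reading the fault is an undefined term. This is plausible, but nothing in the documents states it.

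The evidence that arm affects visits is also thin. C.2 gives no rates, the pilot randomised families for six months whereas this trial randomises visitors, and C.3 starts enrolment after the period of heaviest attrition in order to limit dropout. That weakens the carry-over from the pilot. It does not remove it, since 25% dropout is still expected after entry.

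The illustration can be criticised too. The plan's 200 are the families left after attrition, whereas the first simulation counts dropouts among its 200. Families leaving before month 3 would often lack two measurements and enter only through imputation. Among completers the shift is zero. C.6 also names 6 and 12 months as the follow-up points, so whether month-3 weights count is itself uncertain. The month-3 and month-6 columns are therefore the more relevant ones. These points bear on the size of the effect and leave the mismatch with the stated principle as it is.

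**Conclusion.** The concern holds. C.6 applies an undefined visit count to all analyses, including the primary one, beside an intention-to-treat promise. If visits are counted during the intervention, the estimand becomes an effect at fixed dose.

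Neither the size nor the direction can be derived from the documents, which give no visit counts by arm and no association between visits and outcome. The shift is nil if assignment does not affect visits. On the dropout-based assumptions it is 0 to 0.08 SD (0.07 or less for families reaching month 3), below one standard error. Under the stronger assumed values it reaches 0.20 SD, half of the 0.4 SD pilot effect cited in the power section. It should be fixed before analysis because the primary estimate's meaning is otherwise left open. Confidence is medium, since a pre-entry count may have been intended.

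**What to change.** In C.6, General strategy, strike number of visits from the covariates of the primary and all other total-effect analyses. Add that visits received during the intervention are used only in a separately labelled dose or mediation analysis, with the counting window stated. Stating that window also requires reconciling the 12-month, 18-month and two-year periods given in different sections.

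A visit count may stay in the main models only if it is complete before the family's study entry and COPE start, and could not have been influenced by the visitor's assignment. With rolling entry, this has to be checked family by family.

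One minor alignment: the list also enters home visitor as a covariate, while the statistical models section treats visitor as a Level-2 random effect. State that visitor enters only as that random effect, with visitor experience as a Level-2 covariate.

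The cost is about two sentences, with no change to data collection or sample size. Dropping the term gives up whatever precision visits would add. At the assumed slope of 0.2 that is 1 − √0.96 = 2.0% of the standard error, or 1 − √(0.71/0.75) = 2.7% with the baseline outcome already in the model.
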